This fMRI protocol adopts a similar event-related design developed and validated by Milad et al.^{101,102}, which manipulates context using an ABBA design and will be conducted over 4 study visits. Stimulus parameters will be similar to those conducted by Milad et al.¹⁰². Each “context” will consist of different images of a neutral scene in which the conditioned stimuli will appear. Conditioned stimuli (CSs) will consist of emotionally neutral objects or facial expressions and unconditioned stimuli (US) will be an adverse stimulus (e.g. loud noise¹⁰³; a mild electric shock to the wrist^{36,101,102,104-110}). During all sessions, our primary measures of conditioned fear will be measures of psychophysiological responding via electrodes, as well as US expectancy ratings for each CS trial¹⁰³. All experimental phases (Extinction, Extinction Recall/Fear Renewal), except Fear Acquisition, will be conducted in the fMRI scanner with simultaneous psychophysiological recordings and US expectancy ratings. Fear Acquisition will be conducted in one our testing rooms at the Eugene Applebaum College of Pharmacy & Health Sciences (EACPHS) building.

C.2. Nature of Participant Population: The number of participants expected to participate in the study is 150 [50 patients with PTSD and two controls groups individually matched (age, gender, education): 50 trauma-exposed subjects without PTSD (also matched on trauma-exposure) and 50 non-exposed subjects]. The sample size is required to reach at least 15-20 participants in each experimental group (6 groups). Based on prior experience we expect that data from about 30 participants (5 per group) will be not be usable due to either failure to complete all sessions or poor skin conductance recordings. Participants of both genders will be included in the study and the age range of participants will be from 21-45. Persons below 21 or above 45 are excluded because beyond this range age may influence response to the drugs. Furthermore, the relatively small age range is intended to reduce variation in performance on the behavioral task. There are no enrollment restrictions based upon race or ethnic origin. Candidates will undergo a structured clinical psychiatric interview¹¹¹⁻¹¹³ and will fill out questionnaires related to their general physical health, current medications, with a detailed section on current and lifetime drug and alcohol use.

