C.2.1. Inclusion of Women and Minorities: Women and minorities will be included in the study. Sex/gender, racial/ethnic, or socioeconomic group are not expected to affect the results of the experiments, therefore there are no limitations set on any of these groups for inclusion in the study. Volunteers will not be excluded on the basis of gender or minority/ethnic/racial status. Approximately half of the sample (see below) will be women, and thus, females will be well-represented. Based on Wayne State University’s participant recruitment area, which includes the city of Detroit, Wayne County, and surrounding suburban areas; we plan to recruit and obtain data from a diverse ethnic/racial sample comprised of the following minority composition. According to the U.S. Census Bureau 2012 statistics, the following groups are represented in percent in Wayne County:

Female, 51.9%; White 54.4% (White not Hispanic, 49.8%); Black, 40.1%; Asian, 2.8%, Hispanic/Latino, 4.2%; American Indian and Alaska Native persons, 0.5%; Native Hawaiian and Other Pacific Islander, 0.1%; ≥ 2 races, 2.2% (For reference: <http://quickfacts.census.gov/qfd/states/26/26163.html>).

However, pregnant participants will be excluded from participation because there is insufficient data to assure safety of the fetus during dronabinol exposure, as well as during MRI scanning. In addition, nursing mothers will be excluded from the study because dronabinol is concentrated in and secreted from human breast milk and is absorbed by the nursing baby.

C.2.2. Inclusion of Children: Those under the age of 21 are excluded from this protocol because by definition provided by the National Institutes of Health, these participants are classified as “children” and exclusion of this group eliminates the potential ethical complications of administering dronabinol, a controlled substance, to children. Knowledge as to the effects of this drug in “adults” are limited and no studies have been conducted in children to determine what effects this drug would have, thus making administering this drug to children risky. In addition persons below 21 are excluded because ages below this cutoff may influence response to the drugs and increase variation in performance on the behavioral task.

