C.2.3. Vulnerable Populations: This study will include women of child-bearing potential and college students. However, we will conduct urine pregnancy tests at the screening visit and before each scanning session to make sure that women are not pregnant. In addition, participation of college students in this study is completely voluntary, as it is for all participants, and will not be required by any course.

C.2.4. Recruitment and Attrition Considerations: Participants will be recruited from the WSU Psychiatric Clinic, Wayne State University’s campus, and surrounding community via several sources including: newspaper advertisements, flyers, and webpage advertisements. Current staff in the department and Department of Psychiatry will be informed about the study to pass along the information (in flyer format) to their participants. Once a participant is in contact with the project coordinator, the coordinator will explain the study to the participant and schedule the participant to come in for a screening and orientation session (Visit 1) at the EACPHS building.

C.3. Study Visits

C.3.1. Screening & Study Entry (Visit 1): After the experimenter reviews the consent form with the participant and answers any question he/she may have, the participant will sign the informed consent document. Candidates will undergo a structured clinical psychiatric interview to determine eligibility for the control groups (HC/TEC) or the PTSD group. Milad and colleagues¹¹⁴ have recently reported that a high level of estrodial in women significantly facilitates fear extinction recall as compared to women with low levels of estrodial. Therefore, to control for possible hormonal facilitation during extinction we will schedule women to complete the experimental session approximately 1 week before the onset of menses; when estrogen levels are low. The Health Questionnaire participants complete during the screening visit includes a section that asks women to report when their last menstrual cycle began and the approximate duration of their cycle. We will use this information to schedule women for the experimental session approximately 1 week before the onset of menses. All participants will undergo a urine drug (and pregnancy test for women) at the screening visit and must be negative to enroll in the study.

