C.4.1. fMRI Analysis: Functional data will be processed and analyzed using conventional methods (GLM, event-related design, random effects) with Statistical Parametric Mapping (SPM8; Wellcome Department of Cognitive Neurology, London; www.fil.ion.ucl.ac.uk/spm)¹⁴⁴⁻¹⁴⁷, previously described in our pharmacological fMRI studies^{91,94,148,149} and extinction recall studies^{102,105}. Analysis will implement 2 complementary approaches⁹⁴: 1) a hypothesis-driven anatomically-focused region of interest (ROI)-based analysis; and 2) exploratory whole-brain voxel-wise analysis. Based on our hypotheses, our two main ROIs are vmPFC and HPC; the AMYG, or at least different sub-regions within AMYG, are involved in fear acquisition^{26,36,150} and extinction²⁵, and thus we identify the AMYG as an ROI *a priori*. These anatomically-defined atlas-based ROIs will be based on anatomical landmarks from human atlases¹⁵¹⁻¹⁵³. In addition, vmPFC and HPC activation reported by Milad et al.⁷⁰ will be used to create a 5 mm radius spherical ROI around peak coordinates to examine data in this study for replication. Extracted BOLD percent signal change (PSC) from each ROI, confined to anatomically-based masks, will be subjected to a repeated measures group (PTSD, TEC, HC) x drug (THC, PBO) x stimulus (CS+E, CS+U) omnibus ANOVA during Extinction Recall. We will test for significant ($p < 0.05$) group x drug x stimulus; all significant main effects and interactions will be followed up by post hoc t-tests with an alpha level of 0.05, two-tailed. If appropriate, we will also include age, gender, and other variables (e.g., mood effects) as additional potential covariates in a separate ANCOVA. For the second approach (whole-brain, voxel-wise), we will employ the same ANOVA approach across the entire brain to search for effects in other areas in an exploratory search to generate hypotheses for subsequent study. Statistical maps for the whole brain analysis will be created using a threshold of $p < 0.001$ with a cluster threshold of 10 voxels. Within the ROIs, a small volume threshold ($p < 0.05$, corrected for multiple comparisons) will be used.

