The context-dependent renewal of fear is another factor that can potentially affect the efficacy of exposure therapy. Therefore, the analysis will also test whether THC can induce generalization of extinction across extinction recall (ABB) and renewal (ABA) contexts. We will conduct the same statistical tests on extracted PSC from each ROI, confined to anatomically-based masks, during the Fear Renewal test, as described above for the Extinction Recall test.

We will also look at correlations between BOLD responses in the AMYG, vmPFC, and HPC and the extinction retention index (see below) during Extinction Recall and Fear Renewal tests. In addition, we will implement psychophysiological interaction analyses (PPI)^{40,154,155} to measure task-dependent functional connectivity among the AMYG, vmPFC, and HPC. Separate connectivity analyses will be performed with each group x drug condition (PTSD-THC, PTSD-PBO, HC-THC, and HC-PBO), using vmPFC and HPC as the seed regions followed by between-group connectivity analyses to assess the effect of THC on functional coupling of the vmPFC, AMYG and HPC during Extinction Recall and Fear Renewal.

C.5. Psychophysiology: The primary assessment of fear learning will be a change in SCR, which will be recorded by electrodes attached to the middle phalanges of the second and third digits of the nondominant hand. AcqKnowledge software (BIOPAC Systems) will be used for off-line analysis. We will also obtain subjective US expectancy to the CS+E compared to the CS+U¹⁰³.

C.5.1. Psychophysiological Analysis: SCR for each CS trial will be calculated as described by Milad et al.¹⁰². Extinction recall will be assessed by comparing the mean differential response during the first four trials of the CS+E versus the first four trials of the CS+U. In addition, we will use the “extinction retention index” (ETI) as described by Milad et al.¹⁰² to measure the magnitude of extinction retention. The ETI adjusts the SCR during extinction recall for differences in CR magnitude during acquisition¹⁰⁹. Analyses will be conducted by ANOVA models as above (follow-up t-tests, $\alpha < 0.05$). In addition, we plan to compare and correlate (using Pearson or Spearman rank Correlational analyses) measures of BOLD activation (PSC) and SCR signal to the CS+E vs. CS+U within and across the two contexts/recall and renewal tests.

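### Controls are individually matched to PTSD patients, but the primary ANOVA contains none of the matching factors, so tests of PTSD against controls will be conservative if those factors predict extinction recall

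*Combined protocol and SAP*

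**What the plan says.** Section C.2 sets out 50 PTSD patients and "two controls groups individually matched (age, gender, education", specified as "50 trauma-exposed subjects without PTSD (also matched on trauma-exposure) and 50 non-exposed subjects". It expects about 30 of the 150 participants (5 in each of the six diagnosis-by-drug cells) to give unusable data.

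Section C.4.1 specifies the main region-of-interest analysis as a "repeated measures group (PTSD, TEC, HC) x drug (THC, PBO) x stimulus (CS+E, CS+U) omnibus ANOVA during Extinction Recall", followed by "post hoc t-tests with an alpha level of 0.05, two-tailed". On covariates it says: "If appropriate, we will also include age, gender, and other variables (e.g., mood effects) as additional potential covariates in a separate ANCOVA". For skin conductance, C.5.1 says: "Analyses will be conducted by ANOVA models as above".

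Neither section contains a matched-set term or names education or trauma exposure. C.3.3.1 describes random assignment to dronabinol or placebo without mentioning the matched sets.

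**The concern.** Matching makes the groups alike on the matching factors. If those factors also predict the outcome, members of a matched set are positively correlated, and the difference between group means varies less than independent samples would suggest. An analysis that omits the factors leaves their variance in the error term. It therefore reports a standard error that is too large and tests below the nominal level. The effort of matching is spent, but its gain in precision is not collected.

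The optional ANCOVA does not settle this. Its trigger is undefined, it sits apart from the primary model, and nothing says which result governs if the two disagree. The contrasts at stake are mainly those of Aim 2, where diagnosis is not randomised and PTSD patients are compared with controls.

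**Working it through.** **Inputs.** From C.2, C.6 and D.1: 150 enrolled, 120 usable, 15 to 20 per cell in six cells, effects of d = 0.8 to 1.5, stated power above 90%. From C.4.1: two-sided alpha of 0.05. Assumed, because the documents give no value: a within-set correlation rho of the analysed outcome, taken from 0 to 0.3.

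**The plan's own power figure.** Two-sided two-sample t-test, d = 0.8:
- cell against cell, 15 or 20 each: 56% or 69%;
- diagnostic groups pooled over drug, 30 v 30 or 40 v 40: 86% or 94%;
- PTSD against all controls, 30 v 60 or 40 v 80: 94% or 98%.

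At d = 1.5, cell against cell gives 98% or more. So the figure above 90% holds for larger effects or for most of the pooled contrasts. C.6 does not say which test it means. That is a separate matter; the 40 v 40 contrast is the reference case below.

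**Excess in the standard error.** With n matched pairs and unit variance, the true variance of the mean difference is 2(1 − rho)/n. The unmatched analysis estimates 2/n. The ratio of standard errors is 1/√(1 − rho):
- rho = 0: 1.000 (0%)
- rho = 0.1: 1.054 (5%)
- rho = 0.2: 1.118 (12%)
- rho = 0.3: 1.195 (20%)

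The same ratio compares the unadjusted model with one whose covariates absorb all of rho (residual variance 1 − rho), and that comparison does not need intact sets.

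**Power, unmatched against covariate-adjusted.** The unmatched test was simulated with intact pairs (100,000 runs per setting). The adjusted test uses the noncentral t with effect d/√(1 − rho) and three covariate degrees of freedom.

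| rho | 40 v 40, d = 0.8 | 40 v 40, d = 0.5 | 20 v 20, d = 0.8 |
|---|---|---|---|
| 0 | 94.3% v 94.2% | 60.1% v 59.8% | 69.3% v 69.1% |
| 0.1 | 95.2% v 96.1% | 60.4% v 64.3% | 70.1% v 73.7% |
| 0.2 | 96.1% v 97.7% | 61.1% v 69.4% | 71.1% v 78.5% |
| 0.3 | 96.9% v 98.8% | 61.8% v 75.1% | 72.7% v 83.6% |

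The simulated type I error of the unmatched test falls from 0.05 to about 0.04, 0.03 and 0.02 at rho of 0.1, 0.2 and 0.3.

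**Why not analyse intact sets only.** If 20% are lost independently, 50 × 0.8² = 32 pairs or 50 × 0.8³ = 25.6 trios remain. A paired analysis of 32 pairs has standard error √(2(1 − rho)/32), against √(2/40) for 40 v 40 unmatched. They are equal when 1 − rho = 32/40, so pairing wins only above rho = 0.20. For trios, 1 − rho = 25.6/40 gives 0.36.

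**Which terms matter.** Extinction recall is judged on CS+E against CS+U. With two stimulus levels, the group × stimulus test is a group test on each person's CS+E minus CS+U difference. A covariate main effect cancels from that difference; only a covariate × stimulus term can reduce its error.

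**The case against.** The strongest reply is that rho may be close to zero for the outcome that counts. The within-person CS+E minus CS+U difference already removes additive effects of age, gender and education on overall response level. The retention index in C.5.1 further adjusts for acquisition magnitude, and C.2 narrows the age range to reduce variation. All of this stands. It does not exclude effects of these factors on extinction recall itself, but the documents give no estimate of one.

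It is also true that omitting the factors neither biases the group difference nor inflates type I error. Nor does the breaking of sets show bias: C.2 expects equal loss across cells, and loss unrelated to the matching factors leaves groups balanced on average. With 32 intact pairs in 40 v 40, the unmatched standard error exceeds the estimator's true sampling SD by 1/√(1 − 0.8 rho), or about 4%, 9% and 15% at rho of 0.1, 0.2 and 0.3. The 5% to 20% range applies to the comparison with full adjustment.

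A reader might go further and infer three things that the documents do not support:
- **That the plan ignores sex.** It matches on gender, schedules women by cycle phase, and offers gender as an ANCOVA covariate.
- **That precision is certainly lost.** This needs rho above zero, which is not established.
- **That C.2.1 contradicts C.3.1.** C.2.1 says "Sex/gender, racial/ethnic, or socioeconomic group are not expected to affect the results of the experiments" to justify open enrolment. C.3.1 reports that "a high level of estrodial in women significantly facilitates fear extinction recall as compared to women with low levels of estrodial". That compares women with women, not women with men, so both statements can stand.

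**Conclusion.** The mismatch between design and primary analysis is plain in the text: individual matching in C.2, and no matching factor in the C.4.1 model or its reuse in C.5.1. Its consequence is conditional. The standard errors for Aim 2 contrasts are too large by 0% to about 20% relative to full adjustment, for assumed rho from 0 to 0.3, and the direction is conservative. At the lower end of the plan's effect range, with 40 v 40, the loss of power is at most about 2 points. It reaches about 13 points at d = 0.5, and about 11 points for a 20 v 20 cell contrast at d = 0.8, both at rho = 0.3. These figures assume that the covariates capture all of the within-set correlation, and the unmatched powers assume intact pairs.

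This is a desirable improvement, not a threat to validity. It is worth making because it costs almost nothing if rho is zero, and because it replaces a discretionary covariate analysis with a stated one.

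**What to change.** In C.4.1 and C.5.1:
- Make the primary group × drug × stimulus model include age, gender and education as prespecified covariates, each with its interaction with stimulus.
- For PTSD versus trauma-exposed controls, add trauma exposure in the same way, and name the measure used. It cannot serve in contrasts with the non-exposed group.
- Take the follow-up contrasts from this adjusted model.
- Keep all usable participants; do not restrict to intact matched sets.
- Report the unadjusted ANOVA as a sensitivity analysis, and state that the adjusted model governs.

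Cost: with 120 usable participants and six cells there are 120 − 6 = 114 between-subject degrees of freedom. Three covariates use 3 of them, and the covariate × stimulus terms use 3 of the 114 in the within-subject stratum. Trauma exposure adds one to each in its contrast. Age, gender and education must already be recorded for the matching, so no new data are needed.

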
After screening, if eligible, the participant will continue with an orientation session to explain the procedures and schedule the sessions. Rules and conditions of participation will be carefully explained. We will query participants about any prior history of claustrophobia or anxiety in small spaces. Each subject will complete a detailed questionnaire regarding the presence of any metal implants or metal objects in their body, and other such contraindications for MRI scanning.

C.3.2. Fear Acquisition (Visit 2): During the Fear Conditioning (Context A) phase, there will be two CS+s that will be paired with the US using partial reinforcement. One of these CS+s will be extinguished during the

subsequent extinction phase (CS+E) whereas the other will not (CS+U). The CS+U serves as a within subject, no-extinction control. A third CS will be presented during conditioning *but* never paired with the US (CS-). Assignment of the slide as CS+E or CS+U (paired with US) and CS- (not paired with US) will be counterbalanced across subjects. The US will be delivered immediately following CS+ offset with no delay between the CS+ offset and the US onset. At the beginning of the session subjects will be told to look carefully at the slides because an unpleasant stimulus (US) may follow the slides. They will also be told that they should learn to predict whether the US will occur or not based on which slide was shown. To assess their predictions, subjects will be required to repeatedly rate their US expectancy using a button box on a scale from 1 to 3 (1 = certain that the US will be presented, 2 = certain that the US will not be presented, and 3 = uncertain whether the US will be presented) and subjects will be asked to repeatedly update their rating to reflect their current US expectancy. At the end of the session all participants will be explicitly told to remember what they had learned; in order to strengthen the retention of the CS-US association for the following days. This visit will be conducted at our research laboratory at the EACPHS building.

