C.3.3. Fear Extinction Session with fMRI (Visit 3): At the beginning of this session all participants will undergo an alcohol breathalyzer test, urine drug (and pregnancy for women) test and all must come back negative before entering the fMRI scanner. During Extinction Learning (Context B), subjects will receive unreinforced presentations of the CS+E (no US) and CS-. As during Fear Acquisition, subjects will rate US expectancy and we will record psychophysiological responding. We will also ask participants to give a rating on the Subjective Units of Discomfort Scale (SUDS) at three time points throughout this session: before the session start, in the middle of the extinction session and at the end of the extinction session. This scale is used to measure fear ratings/"subjective" anxiety^{127,128}. This scale will help provide a measure for extinction of subjective fear. Participants will be explained the SUDS scale prior to getting into the scanner. The SUDS will be presented to the participants on the computer screen and the participant will be asked to report where they fall on the scale during that time point. In addition, all participants will complete three other tasks in the MRI scanner following the Extinction Phase:

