C.3.4. Extinction Memory Recall Test, Fear Renewal Test, & Debriefing (Visit 4): To assess extinction retention, we will conduct an Extinction Recall test 24 hours after the Extinction Learning phase, in which participants will be presented with the CS+E, CS+U, and CS- (no US will be delivered) in Context B. Contrasting CS+E and CS+U during extinction recall in Context B will allow us to assess physiological and brain responses that are specific from extinction recall and are independent from recall of conditioning. To test for renewal of fear (context shift from extinction Context B to conditioning A), we will conduct a Fear Renewal test 24 hours after the Extinction Learning phase, in which subjects will be presented with the CS+E, CS+U, and CS- (no US will be delivered) in Context A. At the end of the experimental session the purpose of the study will be explained to participants. This session will take place in the fMRI scanner at Wayne State University.

C.4. fMRI: All MR scanning will be performed on a 3.0 Tesla Siemens Verio whole-body human MRI scanner with an industry leading 32-channel head coil for superior image quality. A high-resolution structural image will provide precise anatomical localization. Whole-brain fMRI blood oxygen-level dependent (BOLD)-related signal measures will be acquired to measure task- and drug-related effects and to minimize susceptibility artifact (signal loss) at the medial temporal lobe (including the AMYG and the vmPFC)¹⁴¹⁻¹⁴³.

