C.6. Power Analysis: We have conducted several power calculations in our previously published work, used to determine the sample sizes proposed here. First we have consistently found that an n of 14-16 HCs and an n of 14-16 PTSD patients provide adequate power to observe: 1) vmPFC and HPC signal differences between groups during extinction recall; and 2) THC’s effects on AMYG and vmPFC activation and functional connectivity in HCs. Given that the effect sizes tested within- and between-groups in previous studies have ranged between moderate – large (Cohen d 0.8-1.5). With the anticipated cohort 15-20 subjects per group (PTSD-THC, PTSD-PBO, TEC-THC, TEC-PBO, HC-THC, HC-PBO), who complete the entire protocol with usable fMRI and SCR data, this number will confer >90% power to detect moderate effect sizes expected from our significance testing.

D. Additional Human Subjects Information

D.1. Probable Duration of the Study: The study is intended to run for 4 years. During this time we expect to collect data from 120 usable subjects.

D.1.1. Proposed Involvement Per Participant: The total time commitment estimated per participant is 11 hours across all study visits. This is broken down below:

Visit 1: Screening and Study Entry: Approximately 3 hours

Visit 2: Fear Acquisition: Approximately 1 hour

Visit 3: Fear Extinction: Approximately 5 hours

Visit 4: Fear Extinction Recall, Fear Renewal Test, and Debriefing: Approximately 2 hours

D.2. Location Where Research is to be Conducted: The informed consent, diagnostic tests, and the fear acquisition behavioral session will be conducted in the research offices located at the EACPHS building. Functional imaging and the extinction learning, extinction recall/fear renewal, and debriefing session will be conducted at the WSU Magnetic Resonance Research Facility (MRRF), located in the basement of Harper University Hospital.

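### The renewal analysis has no phase or context term and follows an unreinforced recall block, so it does not formally test whether THC generalises extinction across contexts

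*Combined protocol and SAP*

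**What the plan says.** C.1 describes a paradigm "which manipulates context using an ABBA design and will be conducted over 4 study visits". Context A is used for acquisition (C.3.2), B for extinction learning (C.3.3), B for recall and A for renewal (C.3.4). Recall and renewal share one visit, which D.1.1 lists as "Visit 4: Fear Extinction Recall, Fear Renewal Test, and Debriefing: Approximately 2 hours".

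On the cues, C.3.2 states: "The CS+U serves as a within subject, no-extinction control". In C.3.3 extinction learning leaves CS+U out: "subjects will receive unreinforced presentations of the CS+E (no US) and CS"- only. At recall (C.3.4), "participants will be presented with the CS+E, CS+U, and CS- (no US will be delivered) in Context B". The renewal test shows the same three cues, again without the US, in Context A.

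On the analysis, C.4.1 says that "the analysis will also test whether THC can induce generalization of extinction across extinction recall (ABB) and renewal (ABA) contexts". The analysis named for this is: "We will conduct the same statistical tests on extracted PSC from each ROI, confined to anatomically-based masks, during the Fear Renewal test". The tests being repeated are a group x drug x stimulus (CS+E, CS+U) ANOVA and its post hoc t-tests, specified for the recall phase. C.5.1 adds a plan to compare and correlate BOLD and SCR responses to CS+E versus CS+U within and across the two contexts. It also limits the SCR recall measure to the first four trials of each CS+.

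**The concern.** There are two separate problems.

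First, generalisation across contexts is a statement about how the drug effect at renewal relates to the drug effect at recall. Running the same ANOVA once on recall data and once on renewal data gives two answers and no test of the relation between them. A significant result in one phase and a non-significant result in the other does not show that the effect differs.

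Second, the recall test is itself a run of unreinforced presentations in Context B, which is how the plan describes extinction learning. By the time renewal starts, CS+U has had unreinforced trials and CS+E has had a further set without drug on board. The CS+E versus CS+U contrast no longer has the meaning it had at recall, and the change from B to A always coincides with being the later block.

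What is at stake is the reading of the renewal result. If the THC-placebo difference is smaller at renewal, it could be because THC-assisted extinction is tied to Context B, or because the recall block brought the arms closer together. The plan as written gives no means of telling these apart.

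**Working it through.** The documents state no figure for the renewal test, so there is nothing to reproduce. The check sets the exposures side by side and then asks what the planned contrast estimates.

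**Step 1: exposure of each cue** (C.3.2, C.3.3, C.3.4)

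| Cue | Visit 2, A | Visit 3, B | Visit 4 recall, B | Visit 4 renewal, A |
|---|---|---|---|---|
| CS+E | paired with US | unreinforced | unreinforced | unreinforced |
| CS+U | paired with US | not shown | unreinforced | unreinforced |
| CS- | never paired | unreinforced | unreinforced | unreinforced |

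Unreinforced blocks completed before recall: CS+E 1, CS+U 0. Before renewal: CS+E 2, CS+U 1. CS+U is a true no-extinction control at recall but not strictly at renewal. The gap between the cues is still one block (2 - 1 = 1), so the contrast keeps some meaning.

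**Step 2: order.** Recall before renewal is inferred from the A-B-B-A sequence and from the listing of Visit 4. C.3.4 gives both tests the same 24-hour interval and does not state the order as a procedure. The only counterbalancing described is the assignment of slides to cues. On this reading, context, order and prior exposure change together for everyone.

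**Step 3: terms in the model.** The repeated ANOVA has group, drug and stimulus. It has no phase or context factor, so drug x phase and group x drug x phase are not estimated. The C.5.1 sentence names neither a model nor an interaction.

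**Step 4: what the drug x stimulus contrast picks up at renewal.** Let U be the CS+U fear response at the start of recall (equal in both arms), and E_P and E_T the CS+E responses under placebo and THC. Let the recall block remove shares u_P and u_T of the CS+U response and e_P and e_T of the CS+E response, with no effect of the context change. Then, with D the THC minus placebo difference in (CS+U - CS+E):

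D = U(u_P - u_T) + E_P(1 - e_P) - E_T(1 - e_T)

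The documents supply none of these values. Purely to show the behaviour of the formula, assume U = 1, E_P = 0.7 and E_T = 0.3, with shares varied from 0 to 75%:

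- No loss: D = 0.7 - 0.3 = 0.40.
- CS+U alone loses 50% in both arms: within-arm contrasts become 0.5 - 0.7 = -0.20 (placebo) and 0.5 - 0.3 = 0.20 (THC), but D = 0.40. An equal CS+U loss cancels.
- Both cues lose 25, 50 or 75% in both arms: D = 0.40 x (1 - share) = 0.30, 0.20 or 0.10. It shrinks but keeps its sign.
- CS+E loses 50% in both arms and CS+U loses 50% (placebo) and 75% (THC): D = (0.50 - 0.75) + 0.35 - 0.15 = -0.05. With the CS+U losses swapped, D = 0.25 + 0.20 = 0.45. The THC-placebo difference in CS+E alone is 0.35 - 0.15 = 0.20 in both cases.

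The randomised drug contrast survives an equal CS+U loss, can shrink when both cues lose response, and is distorted only if CS+U loss differs by arm or responses reach a floor. In every line the context effect was set to zero, so a change in D from recall to renewal does not by itself demonstrate one.

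**The case against.** A reader might infer that the renewal test can show nothing about THC. The documents do not support that. Drug is randomised between subjects and both arms receive the same recall block, so a THC-placebo difference at renewal is a valid randomised contrast. The planned follow-up t-tests could also examine CS+E by drug without relying on CS+U.

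A reader might also infer that CS+U is useless at renewal. C.3.2 defines it relative to the Visit 3 extinction phase, and it still has one unreinforced block fewer than CS+E. If extinction in B transfers poorly to A, which is the premise of a renewal test, CS+U is affected less. The loss of its control status is a matter of degree.

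It would be wrong to say that no cross-context comparison is planned, since C.5.1 mentions one. The fair complaint is under-specification: no model is named, CS+U stays in the contrast, and prior exposure is not addressed.

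Putting a figure on the attenuation is tempting too. The documents give neither a recall trial count nor an extinction rate, and they defer stimulus parameters to a cited study. If the between-subject SD shrank in proportion to the mean, a standardised effect would not shrink at all.

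Finally, Hypotheses 1A to 3C all concern the recall test, and renewal is an additional analysis. That limits the importance of the point but does not remove it, because C.4.1 poses generalisation as a question to be tested.

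**Conclusion.** The concern holds in limited form. The plan states a question about generalisation across recall and renewal but names only a within-phase ANOVA for it. With renewal after an unreinforced recall block in the same visit, CS+U is no longer strictly a no-extinction control, and context is confounded with order and prior exposure. The plan cannot separate transfer of Visit 3 extinction to Context A from further extinction during recall, and a smaller or null renewal effect could be misread as failure to generalise.

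The point applies to the renewal data of every participant and leaves the recall analyses for Aims 1-3 untouched. It rests on recall preceding renewal without order counterbalancing, which the A-B-B-A sequence and the visit listing imply. No numerical attenuation should be attached to it; the values in the working show only how the contrast behaves.

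**What to change.** In C.4.1 and C.5.1:

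- Analyse recall and renewal in one repeated-measures model with phase (context) as a within-subject factor, using early trials in both phases. The first-four-trials rule, now stated only for SCR at recall, could be extended to renewal and to PSC.
- Name drug x phase (x stimulus) and group x drug x phase (x stimulus) as the tests of generalisation. Report estimates with confidence intervals, since a non-significant interaction is not evidence of equal effects.
- At renewal, report the THC-placebo effect on CS+E relative to CS- alongside CS+E versus CS+U, and do not describe CS+U as unextinguished there.
- State that renewal conclusions are conditional on the preceding recall block and the fixed order. The joint model does not remove that confound, so this statement is needed as well.
- If trial counts allow, add the change in CS+E from late recall to early renewal as a sensitivity analysis. It is closer to the context shift itself, but late-recall responses may be at a floor and short blocks may make the windows overlap.

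The cost is some additional modelling, fMRI regressors split by early trials, and somewhat noisier early-trial estimates. CS- also does not remove recall of conditioning as an unextinguished CS+ would. No new data or visits are needed.
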